4.8. Bias

4.8.1. Confounding

Confounding will be handled by using propensity score (PS) methods. In addition, the use of an active comparator design reduce confounding by indication, as most users of the comparator are also likely to have hypertension as the indication for treatment. To further reduce confounding by indication, we will repeat the analyses after restriction to patients without history of heart or kidney disease, which are other indications for ACE-I/ARB use. Although we included a large number of coexisting conditions, life-style factors and co-medication, we cannot exclude the impact of unmeasured confounding, e.g., by severity of condition indication ACE-I/ARB treatment. As we lacked detailed data on severity of heart and renal diseases, we reduced confounding in a subgroup analysis of patients without any history of these diseases.

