4.8.1.1. Propensity score methods

The PS is the probability of being exposed given the covariate pattern for the patient. The PS will be estimated for each patient hospitalization in each of the examined comparisons using a logistic regression model including calendar time and the covariates listed in the Appendix. As we are interested in the average treatment effect in the treated (ATT), we apply PS-weighting using ATT weights to make the number and covariate distribution in the comparison groups resemble that of the ACE-I/ARB users.

8

Overlap in PS distributions will be checked before weighting. Covariate balance will be assessed by standardized differences (SDs), empirical cumulative distribution functions for continuous variables (age and index), and by PS-weight percentiles.

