4.8.2. Selection bias

The risk of selection bias is reduced by including all tested Danish inhabitants. Still, criteria for testing and hospital admission have changed during the study period, which will be addressed in a sensitivity analysis stratified by calendar time. We do not expect that ACE-I/ARB users would be more likely to be tested, and thereby included, as compared to users of other antihypertensive drugs.

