The risk of COVID-19 (a positive test for SARS-CoV-2) will be analyzed using a testnegative case-control design among all patients tested. All covariates will be tabulated for patients with a positive test and negative test for SARS-CoV-2. The odds ratio for current ACE-I/ARB use vs. non-use and CCB use, respectively, will be estimated using two separate logistic regression models adjusted for all covariates, see Appendix.

In a sensitivity analysis, we will explore the robustness of our findings by repeating the analyses in patients who filled a prescription within 120 days before a positive test.

Finally, we will do a sensitivity analysis stratified by calendar time to address changes in testing and hospitalization strategy.

10

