Acute renal replacement therapy (RRT) (in patients without chronic RRT)	DNPR/Procedure		BJFD0	BJFD2 (any codes within prior 12 months)
Treatment with inotropes/vasopressors	DNPR/Procedure		BFHC92A, BFHC92B, BFHC92C, BFHC92D, BFHC92E, BFHC93A, BFHC93B, BFHC93C, BFHC95	
Covariates				
Age	CPR			
Sex	CPR			
Calendar time (before / after lockdown)	DNPR			
Hospital-diagnosed hypertension	DNPR/ICD-10	10y	110, 115	
Stable angina pectoris (without procedures)	DNPR/ICD-10	10y	120, 1251, 1259	121, 122, 123, 1200
Stable angina pectoris or CABG/PCI procedures	DNPR/ICD-10	10y	120, 1251, 1259	121, 122, 123, 1200
	DNPR/Procedure	10y	KFNA, KFNB, KFNC, KFND, KFNE, KFNF, KFNG, KFNH20	I21, I22, I23, I200 (any diagnosis during hospital contact with
				contact the proc

				or within 10
				years before
Myocardial infarction	DNPR/ICD-10	10y	121, 122, 123	
Heart failure	DNPR/ICD-10	10y	150	
Stroke	DNPR/ICD-10	10y	160, 161, 163, 164	
Atrial fibrillation/flutter	DNPR/ICD-10	10y	148	
Heart valve disease	DNPR/ICD-10	10y	105, 106, 107, 108, 109.8, 134-137, 139, 151.1A, Q22, Q23	
Venous thromboembolism	DNPR/ICD-10	10y	126, 1801, 1802, 1803	
Diabetes	DNPR/ICD-10	10y	E10, E11, E12, E13, E14, O24, G63.2, H360, N083	O24.4
	NPD/ATC	10y	A10A, A10B	
Chronic pulmonary disease	DNPR/ICD-10	10y	J40, J41-J44, J45–J47, J60–J67, J68.4, J70.1, J70.3, J84.1, J92.0, J96.1, J98.2, J98.3	
Markers of smoking (diagnoses or medications for tobacco smoking or	DNPR/ICD-10	10y	J41-J44, F17, Z716, Z720	
chronic obstructive pulmonary disease)				
	NPD/ATC	10y	R03, N07BA	
Obesity diagnoses or medications	DNPR/ICD-10	10y	E66	
	NPD/ATC	10y	A08	
Alcoholism-related diagnoses or medication for alcohol deterrent	DNPR/ICD-10	10y	DF10, DE244, DG312, DG621, DG721, DI426, DK292, DK70, DK852, DK860, DQ860, DZ502, DZ714, DZ721	F100
	NPD/ATC	10y	V03AA, N07BB	
Kidney disease diagnosis	DNPR/ICD-10	10y	112, 113, N00–N05, N07, N11, N14, N18–N19, Q61, N08, E102, E112, E142	
End-stage renal disease (kidney transplant or dialysis)	DNPR/Procedure	10y	BJFD2	
	DNPR/Surgery	10y	KKAS	
	DNPR/ICD-10	10y	T861, Z940	
Liver disease	DNPR/ICD-10	10y	B18, B150, B160, B162, B190, I85, K70, K71, K72, K73, K74, K760, K76.6	
Dementia	DNPR/ICD-10	10y	DF00, DF01, DF02, DF03, DG30, DG310B, DG311, DG318, DG319	
	NPD/ATC	10y	N06D	
Cancer (including metastatic cancer)	DNPR/ICD-10	10y	C00-C96, D459, D46, D471, D473, D474, D475, CxxxM	C44
Concurrent antihypertensive medication (see exposures)	NPD/ATC			

Statins	NPD/ATC	90d	C10AA, C10B

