Aspirin	NPD/ATC	90d	B01AC06, N02BA01, N02BA51
Opioid use	NPD/ATC	90d	N02A, N07BC02
Immunosuppressant use	NPD/ATC	90d	L04
Glucocorticoids	NPD/ATC	90d	H02AB
Loop diuretics	NPD/ATC	90d	C03C
Antibiotics	NPD/ATC	10d	J01
Antivirals	NPD/ATC	10d	J05
Vitamin K antagonists	NPD/ATC	90d	B01AA
Antidepressants	NPD/ATC	90d	N06A
Antipsychotics	NPD/ATC	90d	N05A
Hypnotics/sedatives	NPD/ATC	90d	N05C
Marital status	CPR		
Rural/urban place of residence	CPR		

Abbreviations: ATC Anatomical Therapeutic Chemical Classification System; CPR Danish Civil Reigistration System; DNPR Danish National Patient Registry; ICD-10 International Classification of Diseases 10th edition; NPD National Prescription Database.

References:

- 10. Sommerstein R, Gräni C. Rapid response: re: preventing a covid-19 pandemic:

ACE inhibitors as a potential risk factor for fatal Covid-19. https://www.bmj.com/content/368/bmj.m810/rr-2. *BMJ.* 2020.

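### Place enters the models only as rural/urban residence, so other differences between areas are not adjusted for; this matters mainly for the test-negative odds ratio, especially against non-users

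*Protocol*

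**What the plan says.** Section 4.8.1.1 estimates each propensity score "using a logistic regression model including calendar time and the covariates listed in the Appendix". Section 4.9 says that the test-negative odds ratios, against non-use and against CCB use, are "estimated using two separate logistic regression models adjusted for all covariates, see Appendix". I take the Appendix to be the Codes table that follows Section 7.

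That table names its covariates one by one. The only item on place is "Rural/urban place of residence", taken from the civil registration system; its categories are not given. Time appears as "Calendar time (before / after lockdown"), that is, at two levels. No region, municipality, hospital or test-site term appears among the covariates, the subgroups, the sensitivity analyses or the bias sections.

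On testing and admission practice, Section 4.8.2 says that "criteria for testing and hospital admission have changed during the study period, which will be addressed in a sensitivity analysis stratified by calendar time". Section 4.9 repeats this: "we will do a sensitivity analysis stratified by calendar time to address changes in testing and hospitalization strategy". Section 4.8.2 adds: "We do not expect that ACE-I/ARB users would be more likely to be tested, and thereby included, as compared to users of other antihypertensive drugs".

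**The concern.** The study pools everyone tested in the country. Its third aim models a positive result among the tested, and that probability depends on how much virus circulates locally and on who is offered a test. Hospital and ICU admission depend partly on local thresholds. If the rate of ACE-I/ARB treatment, or the choice between ACE-I/ARB and CCB, also differs by area, place confounds the association.

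Neither planned safeguard separates two urban areas with different local epidemics in the same period: a rural/urban term puts them together, and so does a calendar stratum. The statement on differential testing in Section 4.8.2 compares ACE-I/ARB users only with users of other antihypertensives. It does not cover the contrast with non-users, which Section 4.6 lists as a main comparison.

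The covariate list is written into the protocol, so this is a choice already made and not a detail left open for a later analysis plan.

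**Working it through.** The protocol states no figure on this point, so there is nothing to reproduce. The calculations below only give scale.

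**Inputs from Section 4.10.** 96,224 tested and 7,515 positive, so positivity is 7,515/96,224 = 7.8%. Expected use is 17% for ACE-I/ARB and 7% for CCB (from a historical influenza/pneumonia cohort), so the ACE-I/ARB share of the two is 17/(17+7) = 71%.

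**Assumed inputs.** Two areas of equal size, positivity 5% and 11% (mean 8%), and no drug effect within either area.

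**1. Against CCB.** Assume ACE-I/ARB shares of 68% and 74% (mean 71%). Per 1,000 tested users of either drug in each area:

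- ACE-I/ARB positives: 680 × 0.05 + 740 × 0.11 = 34.0 + 81.4 = 115.4 of 1,420 (8.13%)
- CCB positives: 320 × 0.05 + 260 × 0.11 = 16.0 + 28.6 = 44.6 of 580 (7.69%)
- Crude OR = (115.4/1,304.6)/(44.6/535.4) = **1.06**

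With equal shares in both areas the OR is 1.00. Shares of 66% and 76%, a gap of 10 points instead of 6, would be needed to reach about 1.1: (116.6/1,303.4)/(43.4/536.6) = 1.11.

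**2. Against non-users.** Assume 15% and 19% ACE-I/ARB use (mean 17%), with everyone else counted as a non-user. Per 1,000 tested in each area:

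- Users: 150 × 0.05 + 190 × 0.11 = 28.4 of 340
- Non-users: 850 × 0.05 + 810 × 0.11 = 131.6 of 1,660
- Crude OR = (28.4/311.6)/(131.6/1,528.4) = **1.06**

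**3. A wider range.** For one omitted binary factor, the bias factor is [pE(g − 1) + 1]/[pU(g − 1) + 1]. Here g is the relative odds of the outcome in a high-intensity area, and pE and pU are the shares of exposed and comparator patients living there. With pU = 0.33:

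| g | pE = 0.33 | pE = 0.30 | pE = 0.25 |
|---|---|---|---|
| 1.5 | 1.00 | 0.987 | 0.966 |
| 2 | 1.00 | 0.977 | 0.940 |
| 3 | 1.00 | 0.964 | 0.904 |

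The distortion is between 0 and about 10%, and it can go in either direction.

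**4. Against the precision of the study.** Apply the 17% and 7% to 7,515 positives and 96,224 − 7,515 = 88,709 negatives. The crude standard error of the log OR is the square root of the sum of the reciprocal cell counts:

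- Non-users (other 83%): √(1/1,278 + 1/6,237 + 1/15,081 + 1/73,628) = 0.032. The bias is ln(1.0585) = 0.057, or about 1.8 standard errors.
- CCB users (7%): √(1/1,278 + 1/526 + 1/15,081 + 1/6,210) = 0.054. The bias is ln(1.062) = 0.060, or about 1.1 standard errors.

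Adjusted standard errors would be larger, so these ratios are upper illustrations.

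**The case against.** The strongest reply is that this is a request for one more covariate. The list already covers demographics, many diagnoses, co-medication, marital status, calendar time and rural/urban residence, and Section 4.8.1 admits that "we cannot exclude the impact of unmeasured confounding, e.g., by severity of condition indication ACE-I/ARB treatment". No regional difference in prescribing, testing or ICU practice is documented, and the Background describes the Danish tax-funded health system as uniform. The illustration uses invented inputs and a crude odds ratio, so it is not the residual bias of the planned, adjusted estimate.

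Much of this stands. The premise is unproven, the numbers show scale only, and the active comparator should weaken the problem against CCB users. What does not fall is the observation itself: the models as specified cannot separate areas beyond rural/urban status, and no planned analysis would show whether the results depend on place. Uniform financing does not make local virus circulation uniform.

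Three stronger readings are tempting and are not supported:

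- A reader might infer that Section 4.8.2 admits differences between places and then leaves them unhandled. It mentions only change over time, and it provides an analysis for that.
- A reader might infer that place is wholly uncontrolled. Rural/urban residence is a partial proxy.
- A reader might infer that the mortality result is compromised. The mechanisms here are positivity among the tested and admission or ICU thresholds, and 30-day death depends on them far less directly.

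**Conclusion.** The point holds as a modest gap in adjustment. It applies first to the test-negative odds ratio, chiefly the contrast with non-users, then to hospital and ICU admission, and hardly to the primary outcome.

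On assumed inputs the spurious odds ratio is about 1.06, within an illustrative range of 0 to about 10% in either direction. It is exactly null if ACE-I/ARB use is unrelated to area given the other covariates. The protocol cannot settle which case applies. The change is a worthwhile low-cost improvement. It is not a correction of an error that would overturn a result, and confidence in a material bias is low.

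**What to change.** 1. Confirm that region of residence is in the linked extract. Residence comes from the civil registration system, but the protocol does not say at what geographic level it is available.
2. Add broad region, and region by calendar period, to both test-negative logistic models. Keep the rural/urban term.
3. For hospital and ICU admission, either add broad region to the propensity score or run a region-adjusted or region-stratified sensitivity analysis alongside the calendar-time one.
4. The mortality analysis need not change. If area drives prescribing but hardly affects death, region in that propensity score would cost precision without removing bias.

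The cost is a few indicator variables and a small loss of precision. With, say, five regions (an assumed number) and the two-level calendar term, each test-negative model gains 4 + 4 = 8 parameters. The CCB model would have roughly 0.24 × 7,515 ≈ 1,800 positives if the Section 4.10 shares apply. Finer areas risk sparse cells, so the regions should stay broad.

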For each question of the Checklist, the investigator should indicate whether or not it has been addressed in the study protocol. If the answer is "Yes", the section number of the protocol where this issue has been discussed should be specified. It is possible that some questions do not apply to a particular study (for example, in the case of an innovative study design). In this case, the answer 'N/A' (Not Applicable) can be checked and the "Comments" field included for each section should be used to explain why. The "Comments" field can also be used to elaborate on a "No" answer.

This Checklist should be included as an Annex by marketing authorisation holders when submitting the protocol of a non-interventional post-authorisation safety study (PASS) to a regulatory authority (see the Guidance on the format and content of the protocol of non-interventional post-authorisation safety studies). The Checklist is a supporting document and does not replace the format of the protocol for PASS presented in the Guidance and Module VIII of the Good pharmacovigilance practices (GVP).

Study title: Renin-angiotensin-aldosterone system inhibitors and adverse outcomes of COVID-19: a Danish nationwide cohort study

EU PAS Register[®] number: Study reference number (if applicable):

Sec t	ion 1: Milestones	Yes	No	N/A	Section Number
1.1	Does the protocol specify timelines for				
	1.1.1 Start of data collection ¹	\square			1
	1.1.2 End of data collection ²	\square			1
	1.1.3 Progress report(s)			\square	

¹ Date from which information on the first study is first recorded in the study dataset or, in the case of secondary use of data, the date from which data extraction starts.

² Date from which the analytical dataset is completely available.

Section 1: Milestones	Yes	No	N/A	Section Number
1.1.4 Interim report(s)			\boxtimes	
1.1.5 Registration in the EU PAS Register $^{ m extsf{ iny R}}$	\bowtie			1
1.1.6 Final report of study results.	\square			1

Sect	Section 2: Research question			N/A	Section Number
2.1	Does the formulation of the research question and objectives clearly explain:				
	2.1.1 Why the study is conducted? (e.g. to address an important public health concern, a risk identified in the risk management plan, an emerging safety issue)	\boxtimes			2
	2.1.2 The objective(s) of the study?	\square			3
	2.1.3 The target population? (i.e. population or subgroup to whom the study results are intended to be generalised)	\boxtimes			2
	2.1.4 Which hypothesis(-es) is (are) to be tested?	\boxtimes			2
	2.1.5 If applicable, that there is no a priori hypothesis?			\boxtimes	
Comn	nents:				

Sec t	ion 3: Study design	Yes	Νο	N/A	Section Number
3.1	Is the study design described? (e.g. cohort, case- control, cross-sectional, other design)	\square			4.1
3.2	Does the protocol specify whether the study is based on primary, secondary or combined data collection?	\boxtimes			4.3
3.3	Does the protocol specify measures of occurrence? (e.g., rate, risk, prevalence)	\boxtimes			4.9
3.4	Does the protocol specify measure(s) of association? (e.g. risk, odds ratio, excess risk, rate ratio, hazard ratio, risk/rate difference, number needed to harm (NNH))	\boxtimes			4.9
3.5	Does the protocol describe the approach for the collection and reporting of adverse events/adverse reactions? (e.g. adverse events that will not be collected in case of primary data collection)				7

Sect	tion 4: Source and study populations	Yes	No	N/A	Section Number
4.1	Is the source population described?	\square			4.4
4.2	Is the planned study population defined in terms of:				
	4.2.1 Study time period	\square			4.2
	4.2.2 Age and sex	\square			4.1 (all)
	4.2.3 Country of origin	\square			4.1
	4.2.4 Disease/indication	\square			4.4
	4.2.5 Duration of follow-up	\square			4.5
4.3	Does the protocol define how the study population will be sampled from the source population? (e.g. event or inclusion/exclusion criteria)				4.4

Sect	ion 5: Exposure definition and measurement	Yes	No	N/A	Section Number
5.1	Does the protocol describe how the study exposure is defined and measured? (e.g. operational details for defining and categorising exposure, measurement of dose and duration of drug exposure)	\boxtimes			4.6
5.2	Does the protocol address the validity of the exposure measurement? (e.g. precision, accuracy, use of validation sub-study)	\boxtimes			4.6
5.3	Is exposure categorised according to time windows?	\boxtimes			4.6
5.4	Is intensity of exposure addressed? (e.g. dose, duration)	\boxtimes			4.6
5.5	Is exposure categorised based on biological mechanism of action and taking into account the pharmacokinetics and pharmacodynamics of the drug?	\boxtimes			4.6
5.6	Is (are) (an) appropriate comparator(s) identified?				4.6
Comm	nents:				

Sect	ion 6: Outcome definition and measurement	Yes	No	N/A	Section Number
6.1	Does the protocol specify the primary and secondary (if applicable) outcome(s) to be investigated?	\boxtimes			4.7
6.2	Does the protocol describe how the outcomes are defined and measured?	\boxtimes			4.7
6.3	Does the protocol address the validity of outcome measurement? (e.g. precision, accuracy, sensitivity, specificity, positive predictive value, use of validation substudy)	\boxtimes			4.7
6.4	Does the protocol describe specific outcomes relevant for Health Technology Assessment? (e.g. HRQoL, QALYS, DALYS, health care services utilisation, burden of disease or treatment, compliance, disease management)			\boxtimes	

Sect	ion 7: Bias	Yes	No	N/A	Section Number
7.1	Does the protocol address ways to measure confounding? (e.g. confounding by indication)	\boxtimes			4.8.1
7.2	Does the protocol address selection bias? (e.g. healthy user/adherer bias)	\boxtimes			4.8.2
7.3	Does the protocol address information bias? (e.g. misclassification of exposure and outcomes, time-related bias)	\boxtimes			4.8.3

Comments:

Sect	ion 8: Effect measure modification	Yes	No	N/A	Section Number
8.1	Does the protocol address effect modifiers? (e.g. collection of data on known effect modifiers, sub-group analyses, anticipated direction of effect)	\boxtimes			4.9

Sect	ion 9: Data sources	Yes	No	N/A	Section Number
9.1	Does the protocol describe the data source(s) used in the study for the ascertainment of:				

Sect	tion 9: Data sources	Yes	No	N/A	Section Number
	9.1.1 Exposure? (e.g. pharmacy dispensing, general practice prescribing, claims data, self-report, face-to-face interview)	\boxtimes			4.6
	9.1.2 Outcomes? (e.g. clinical records, laboratory markers or values, claims data, self-report, patient interview including scales and questionnaires, vital statistics)	\boxtimes			4.7
	9.1.3 Covariates and other characteristics?	\square			4.8.1, Appendix
9.2	Does the protocol describe the information available from the data source(s) on:				
	9.2.1 Exposure? (e.g. date of dispensing, drug quantity, dose, number of days of supply prescription, daily dosage, prescriber)				4.6
	9.2.2 Outcomes? (e.g. date of occurrence, multiple event, severity measures related to event)				4.7
	9.2.3 Covariates and other characteristics? (e.g. age, sex, clinical and drug use history, co-morbidity, co-medications, lifestyle)				4.8.1, Appendix
9.3	Is a coding system described for:				
	9.3.1 Exposure? (e.g. WHO Drug Dictionary, Anatomical Therapeutic Chemical (ATC) Classification System)	\boxtimes			4.6
	9.3.2 Outcomes? (e.g. International Classification of Diseases (ICD), Medical Dictionary for Regulatory Activities (MedDRA))	\boxtimes			4.7
	9.3.3 Covariates and other characteristics?	\square			Appendix
9.4	Is a linkage method between data sources described? (e.g. based on a unique identifier or other)	\boxtimes			4.3

Section 10: Analysis plan	Yes	No	N/A	Section Number
10.1 Are the statistical methods and the reason for their choice described?	\boxtimes			4.8.1.1, 4.9
10.2 Is study size and/or statistical precision estimated?	\square			4.10
10.3 Are descriptive analyses included?	\square			4.9
10.4 Are stratified analyses included?	\square			4.9
10.5 Does the plan describe methods for analytic control of confounding?				4.8.1, 4.9
10.6 Does the plan describe methods for analytic control of outcome misclassification?		\boxtimes		

Section 10: Analysis plan	Yes	No	N/A	Section Number
10.7 Does the plan describe methods for handling missing data?		\boxtimes		
10.8 Are relevant sensitivity analyses described?	\boxtimes			4.9

Section 11: Data management and quality control	Yes	No	N/A	Section Number
11.1 Does the protocol provide information on data storage? (e.g. software and IT environment, database maintenance and anti-fraud protection, archiving)	\boxtimes			5
